# 8.1 PRETREATMENT EVALUATION

• Pretreatment biopsy must confirm diagnosis of non-anaplastic non-medullary thyroid cancer prior to treatment. A core biopsy may be obtained from the primary tumor or regional lymph node metastases. If the diagnostic biopsy was performed outside of MSKCC, and tissue cannot be obtained, a repeat core biopsy may be required.

## Within 8 weeks prior to start of treatment

- Electrocardiogram as per institution standard
- Standard pretreatment dental evaluation and initiation of dental prophylaxis (unless patient is edentulous)
- FDG PET/CT with calculation of metabolic tumor volume
- Recommended research MRI

# Within 30 days prior to start of treatment:

- Complete medical history including current medications, and physical examination including evaluation of Karnofsky Performance Status
- The following laboratory studies: Complete blood count with white blood cell differential and platelet counts; Comprehensive Metabolic Panel.
- Baseline TSH, T3, T4, thyroglobulin
- Mandatory pre-treatment evaluation in the Speech and Swallowing Center with Standard objective measures of pre-treatment swallow evaluation using Modified Barium Swallow Impairment Profile (MBSImP) and Penetration-Aspiration scale

## Within 14 days prior to the start of treatment

- Serum pregnancy test for women of childbearing potential within 14 days prior to therapy.
- Complete blood count with white blood cell differential and platelet counts; Comprehensive profile (including electrolytes, bicarbonate, blood urea nitrogen (BUN), creatinine, glucose, alkaline phosphatase, aspartate aminotransferase (AST), alanine aminotransferase (ALT), total bilirubin, total protein, albumin, and glucose); magnesium level; prothrombin time with INR, and activated partial thromboplastin time.

# 9.1 TREATMENT/INTERVENTION PLAN

All patients will undergo radiation treatments using IMRT with concurrent low-dose radiosensitizing doxorubicin at 10 mg/m^2 will be administered as per standard MSKCC guidelines.

Exploratory analyses will be performed on the standard care pre-treatment biopsy.

# 9.2 Radiation Therapy Treatment Plan

### 9.2.1 External beam equipment and techniques

6 MV photon beams produced will be used to deliver computer controlled multi-segmental therapy with multi-leaf collimators (MLCs) in dynamic mode. The number of fields will be determined by the treatment planning system. All fields will be treated each day. Portal images will be taken of each field. The accuracy of patient position and MLC aperture will be monitored weekly by portal images for selected fields.

## 9.2.2 Standard treatment planning

Treatment will be directed to the primary tumor and bilateral cervical lymph nodes, if applicable. The target volumes and normal tissue structures will be defined using CT (or MRI) and PET images. Patients will be simulated in the treatment position with individualized Aquaplast immobilization masks. All patients will undergo standard of care positron emission and computed tomography (PET/CT) simulation for treatment planning. If a FDG PET/CT was already performed as part of the pretreatment workup, the investigator can fuse the FDG PET/CT with the CT portion of the radiation simulation as per standard of care guidelines in the department of radiation oncology. Standard uptake value, metabolic tumor volume, and total lesion glycolysis from PET/CT scans will be reported. A CT scan with slices of 3mm thickness or less will be acquired through the target region. A margin of 5-10 cm superior and inferior to the target will be scanned with slices of 5mm thickness or less. All patients will be treated with standard IMRT plans. The volumes of interest will be identified on each axial CT slice. GTV will consist of the gross primary tumor and involved lymph nodes. A high risk subclinical clinical target volume (CTV high risk) as well as a lower risk subclinical volume (CTV low risk) will be defined according to the risk associated with the disease site. A planning target volume (PTV) will also be defined to account for biologic and technical uncertainties. Normal structures of interest including the spinal cord, parotid glands, submandibular glands, oral cavity, and larynx will be outlined in 3 dimensions.

The CT data will be transferred to the 3D treatment planning system. A plan using multiple beams will be tailored to the patient's anatomy and disease distribution. The method of inverse-planning will be utilized to determine the intensity profiles of the treatment beams. All dose constraints, maximum, mean, and minimum are standard as per our MSKCC treatment planning guidelines for patients undergoing IMRT for their thyroid cancer.

#### 9.2.3 Treatment schedule

Treatment will be delivered as one fraction per day on a standard 5 day per week schedule (excluding weekends and holidays), to a total dose of 7000 cGy. Each radiation treatment will last approximately 15 to 30 minutes. If the patient misses a scheduled treatment, this treatment will be added on the end of the treatment plan.

#### 9.2.4 Treatment delivery

Photon beams with an energy of 6 MV will be used to deliver computer controlled multisegmental therapy, and multileaf collimators in a dynamic mode will be used to produce the intensity modulated treatments. Electron beams may also be used if clinically indicated.

#### 9.2.5 PEG tube

PEG placement is optional, if the investigator determined that PEG tube placement is appropriate either prior to or during IMRT.

### 9.2 Chemotherapy

**9.2.1** Radiosensitizing low dose doxorubicin at 10 mg/m^2 will be administered weekly. Dose reduction or missed scheduled chemotherapy session will be dealt with at the treating physician's discretion.

Every attempt will be made to administer treatment on schedule. Doxorubicin may be given up to 3 days before or after the scheduled dates, if necessary for medical or personal reasons.

Guidelines regarding dose delays and/or reductions are provided in Section 11. Reasons for such changes will be outlined in the medical record.

**9.2.2** Complete blood cell count should be obtained within 48 hours prior to each scheduled chemotherapy treatment date.

Dose recalculation by weight is only required if the weight has change by > 10% from the BSA being used.

Day 1 refers to the first day of IMRT.

**9.2.3** Day 1 : During week 1 of IMRT, patients will receive doxorubicin 10 mg/m^2 intravenously. The weekly start day of doxorubicin 10 mg/m^2 will be at the discretion of the treating physician. Recommended anti-emetic administration will be given per MSKCC Guidelines but may be given as per the treating physician's discretion.

Note in clarification regarding MD clinic visits: Patients should be seen by an MD in clinic weekly during chemoradiation. Missed visits for reasons such as inpatient admission, logistical difficulties, or other medical reasons will be addressed on a case by case basis by the Principal Investigator and/or Treating Physician.

#### 9.3 Specimen Collection and Tissue Banking and Translational Research

#### Mutational profile of the tumors:

As part of the main consent patients will consent to required pre-treatment tissue analysis. This analysis will only be required for those patients who have sufficient tissue available.

General sequence of events after tissue is obtained: [name] will mark the regions of the slides enriched for tumor cells. [name] lab will then dissect the tissue from the slide and send the samples to Beene Core for DNA isolation and mass spectroscopy. [name] lab will analyze the traces and perform confirmatory sequencing if needed to clarify ambiguous cases. Tissue will be stored at [name] laboratory.

In detail, to evaluate the molecular profile in these patients, 6 sections of 10 microns from formalin-fixed paraffin embedded primary or recurrent tumor tissue will be subjected to DNA extraction and mutation detection as previously described [34]. Briefly, a Mass spectrometry Sequenom–based genotyping assay (Sequenom Mass array; Sequenom, San Diego CA) platform for thyroid carcinomas developed at MSKCC by [name] laboratory will be used

for mutation analysis. The latter consists of 116 assays, to interrogate mutations in 16 genes, including the most common thyroid oncogenes such as *BRAF, NRAS, HRAS, KRAS, PIK3CA, and AKT1*. As the mass spectrometry genotyping assays for codons 12 and 13 of *HRAS* are not informative in this platform, all the tumors that are wild type for *BRAF or RAS* mutations will be sequenced using primers designed for this regions (codon 12 and 13 of *HRAS*) [34]. All these mutation analysis will be performed at MSKCC in [name] laboratory and MSKCC core facilities.

# **10.1 EVALUATION DURING TREATMENT/INTERVENTION**

## **10.1 Evaluation during IMRT**

Patients will be assessed at weekly status check as per institutional standard practice. At the weekly assessments patients will have a limited physical exam, KPS evaluation, and toxicity assessments. CBC will also be completed weekly during treatment. A recommended DW and multiparametric MRI should also take place approximately weekly unless contraindicated for patients.

### 10.2 Follow-up after IMRT

**10.2.1** Clinic visits will take place approximately every 3 months for 2 years, approximately every 6 months for the next 3 years, and approximately annually thereafter with Radiation Oncology and/or Medical Oncology. This schedule may be altered, as clinically indicated.

Patients who are removed from study for toxicity (but who maintain active follow-up) will be followed according to the same post-treatment surveillance plan as patients who complete study treatment. The following will be completed at these visits: physical exam, KPS assessment, toxicity assessment (according to NCI CTCAE v 4.0)

**10.2.2** Three months (+/- 4 weeks) after completion of IMRT, radiologic assessment will be performed. This will include a diagnostic FDG PET/CT scan, along with a recommended CT and/or MRI scan of the primary tumor/neck, mean and maximum standardized uptake value, metabolic tumor volume, and total lesion glycolysis will be recorded prospectively for all FDG PET/CT scans. The MRI scan may be performed in addition to the CT scan, or instead of the CT scan, as clinically indicated. Imaging will then be repeated at 6 months (+/- 4 weeks) post-RT and then every 6 months (+/- 6 weeks) until 2 years post-RT. The DW and multiparametric MRI will be recommended for 3 months, 6 months, and then every 6 months (all +/- 4 weeks) until 2 years post-RT unless contraindicated for main campus patients only.

**10.2.3** Patients will be advised to undergo routine surveillance dental exams approximately 4 to 8 months after completion of definitive locoregional therapy. The dental visit dates may vary due to logistical considerations, but all patients will be advised to maintain dental follow up. Assessments of salivary flow may be performed at dental visits, but are not mandatory. Additional dental evaluations may be performed, as clinically indicated.

**10.2.4** Mandatory post-treatment evaluation in the Speech and Swallowing Center with Standard objective measures of pre-treatment swallow evaluation using Modified Barium Swallow Imp and Penetration-Aspiration scale. **(See Appendix 1).** Speech and Swallowing assessment should be performed at baseline, and after radiation at approximately 6 months, 12 months, 18 months, and 24 months post treatment.

	Pre-Rx (w ithin 30 days prior to RT unless otherw ise indicated)	Weekly during RT	Follow up (Q3 mos until 2yrs, Q 6 mos until 5yrs; annually thereafter)
Confirmation of Non- Anaplastic Non-Medullary Thyroid Cancer a	Х		
Collection of tumor tissue for translational research if available a	Х		
H & P by MD	Х	Xp	Х
KPS	Х	Х	Х
CBC	Х	Х	
Comprehensive Metabolic Panel	Х		
TSH, Thyroglobulin, T3, T4	Х		
EKG	Xc		
Recommended CT and/or MRI of the neck with contrast	X		Xď
Recommended DW and multiparametric MRI unless contraindicated for patients	Xc	Х	Xď
FDG PET/CT	Xc		
Pregnancy Test (for women of child bearing potential)	Xe		
Speech and Swallowing Evaluation	Х		Xţ
Dental Evaluation (unless patient is edentulous)	Xc		Xa
Low dose radiosensitizing doxorubicin (10 mg/m  )		Х	

IMRT		X h	
AE monitoring i		Х	Х
Co-morbidities	Х		

- a) Any time prior to RT start
- b) Weekly status check
- c) Within 8 weeks of RT start
- d) At 3 months (+/- 4 weeks) and 6 months (+/- 4 weeks), and then every 6 months (+/- 8 weeks) until 2 years
- e) Within 14 days of RT start
- f) Performed after radiation at approximately 6 months, 12 months, 18 months, and 24 months post-treatment.
- g) At approximately 4-8 months post-RT only
- h) Daily except for weekends and holidays
- i) AEs will be assessed according to CTCAE v 4.0 throughout the treatment course and in follow up.
- j) Pre-treatment MRI to be completed within 8 weeks prior to treatment start, if recommended

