A retrospective review of 66 patients with gross residual or unresectable non-anaplastic nonmedullary thyroid cancer that underwent EBRT with or without low dose concurrent chemotherapy at Memorial Sloan-Kettering Cancer Center showed that the 3-year locoregional progression-free survival rate was 77.3%, with a 3-year overall survival rate of 54.4%. [51]. The median radiation dose was 6630 cGy (Interguartile range 6000-7000cGy). Concurrent low dose radiation sensitizing chemotherapy was administered to 21 of the 66 patients (31.8%) with a non-significant increase in the 3-year locoregional progression-free survival rate (90.0% versus 73.0%). Despite this improvement in local control, there was no difference in the median overall survival (43.1 versus 37.1 months) likely secondary to the fact that patients treated with concurrent chemotherapy had larger volume of disease and a greater incidence of poorly differentiated histology both of which are known negative prognostic factors. These promising results were in a heterogeneous cohort of patients with multiple poor prognostic risk factors, majority of whom had RAI refractory disease. This is the only published series focused on patients with gross residual or unresectable disease. Grade 3 acute mucositis and dysphagia occurred in 11 (16.7 %) and 13 (19.7 %) patients, respectively. The addition of concurrent chemotherapy only resulted in a 10% increase in acute grade 3 hoarseness (10% versus 0%), with no differences in acute or late toxicities for dermatitis, dysphagia, mucositis, nausea, vomiting, fatigue, or need for a reactive feeding tube. Late adverse toxicity was notable for percutaneous endoscopic gastrostomy tube use in 4 patients (6.1 %), though 2 of these patients had the percutaneous endoscopic gastrostomy tube placed prior to EBRT. There was no difference in the late toxicities between EBRT and CCRT patients including hoarseness and need for a feeding tube. Although patients with metastatic disease fared worse than patients with localized thyroid cancer, loco-regional control was still achieved in a significant number of patients (61.4% versus 88.4%). Thus, EBRT should be considered, even for patients with metastatic disease, because progression in the thyroid bed or neck can cause significant morbidity. Thus our update of the MSKCC experience demonstrated that in patients with unresectable disease or gross residual disease, the 3 year locoregional progression-free interval was 73.0% in patients treated with EBRT alone and 90.0% in patients who underwent concurrent low dose radiation sensitizing chemotherapy with only a slight increase in hoarseness that was self resolving.

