# 11.0 TOXICITIES/SIDE EFFECTS

During radiation, adverse events will be graded using the NCI Common Terminology Criteria for Adverse Events—Version 4.0. A copy of the CTCAE version 4.0 can be downloaded from the CTEP home page (http://ctep.info.nih.gov).

Treatment modifications are based on CTCAE version 4.0. Once a patient has had a doxorubicin dose reduction for toxicity, the dose will not be re-escalated.

Reproductive risks: There is a risk of birth defects associated with this study. Patients must use birth control while on this study. Women should not breastfeed while on this study.

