#### 11.1 Radiation Therapy-Associated Adverse Events

Reversible radioepithelitis of pharyngeal mucosa is expected and its timing with dose and severity will be noted and graded according to NCI CTCAE v4.0. Epilation of treated areas and various degrees of skin reaction are expected. Other expected acute reactions include hypogeusia, dysphagia, thick saliva, hoarseness, radiation dermatitis, nausea, vomiting, anemia, fatigue, and weight loss.

Late toxicities are those that occur at least 3 to 4 months post radiation. Late effects may include permanent xerostomia, hypogeusia, dysphagia, ototoxicity, nasal dryness, serous otitis media, dental decay, hypothyroidism, dysphagia, and trismus. Osteoradionecrosis may occur in 5% or less of patients, but can be reduced by dental evaluation before radiation.

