## **14.0 BIOSTATISTICS**

The primary objective of this study is to determine the 2-year loco-regional progression-free rate. Current literature showed that the 2-year loco-regional progression-free rate is about 40% [16-24]. We expect to improve this rate substantially to 90% by applying the proposed chemoradiation treatment strategy. It should be mentioned that according to previous versions of the protocol 8 patients had been treated with IMRT alone. But prospectively we will treat patients with the current standard which is chemoradiation. To this end we will still employ a single-stage binomial design. We will recruit 19 patients, and we will claim the proposed treatment promising when at least 14 patients are without progression of disease at 2 years from the end of the treatment. This decision rule gives a power (that is, probability of declaring success when the true 2-year progression rate is 90% or higher) of 0.99 with the

type 1 error rate (that is, probability of declaring success when the true 2-year progression rate is 40% or lower) less than 0.01. Patients who died due to any reason, or were lost to F/U within 2 years will be regarded as having loco-regional progression. Patients who do not complete treatment due to excessive toxicity will be excluded from the primary endpoint analysis and replaced by new eligible patients. We expect to accrue the total of 19 analyzable patients in 2 years. The 8 patients who had received IMRT alone will not be counted towards this endpoint and will be summarized separately.

To better understand the loco-regional progression we will also use the cumulative incidence function for summaring the endpoint of time to loco-regional failure, which will be carried out by a competing risks anlaysis. Overall survival rates will be assessed by Kaplan-Meier method. Rates of (acute or late) toxicities will be computed by sample proportions and confidence intervals will also be provided. Summary statistics and/or longitudinal plots for the Modified Barium Swallow-Imp and Penetration-Aspiration scales will be supplied for assessing objective measures of late dysphagia. BRAF and other mutation measurements at baseline will be correlated with clinical outcomes such as overall survival and local-regional control using survival analysis tools. All secondary endpoints will be analyzed for the 19 patients under chemoradiation. The 8 patients who had received IMRT alone will be summarized separately.

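### No CTCAE grade is scheduled before radiation and no rule separates pre-existing from new or worsened conditions, so the crude toxicity rates may include baseline dry mouth, hoarseness and feeding tubes

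*Combined protocol and SAP*

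**What the plan says.** **When toxicity is graded.** Section 11.0 opens with "During radiation, adverse events will be graded using the NCI Common Terminology Criteria for Adverse Events—Version 4.0". The schedule table in Section 10.2 has a row for adverse event monitoring. It is marked under the weekly and follow-up columns and blank under the pre-treatment column. The footnote to that row reads "AEs will be assessed according to CTCAE v 4.0 throughout the treatment course and in follow up". Follow-up visits include "physical exam, KPS assessment, toxicity assessment (according to NCI CTCAE v 4.0").

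**What counts as late.** Section 11.1: "Late toxicities are those that occur at least 3 to 4 months post radiation". The definition does not require the condition to be new or worse than before treatment.

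**How the rates are computed.** Section 14.0: "Rates of (acute or late) toxicities will be computed by sample proportions and confidence intervals will also be provided". The denominator is given in the same section: "All secondary endpoints will be analyzed for the 19 patients under chemoradiation". The 8 patients treated with IMRT alone are summarized separately.

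**What is collected before treatment.** Section 8.1 requires a medical history, a physical examination, a dental evaluation and a mandatory swallowing evaluation (MBSImP and Penetration-Aspiration scale). The schedule table adds a co-morbidities entry. No symptom grade, voice measure, dry-mouth measure or tube-status field is named. Salivary flow appears only in Section 10.2.3, as an optional item at dental visits after treatment.

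**Feeding tubes.** Section 9.2.5: "PEG placement is optional, if the investigator determined that PEG tube placement is appropriate either prior to or during IMRT".

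**The concern.** Section 1.0 gives prospective capture of acute and late toxicity as a purpose of the protocol, and Section 2.0 makes it two secondary objectives, with late dry mouth and dysphagia named. Eligibility (Section 6.2) requires disease that is grossly recurrent after surgery or unresectable, and Section 3.0 stresses how close such disease lies to the larynx and esophagus. Section 6.3 does not exclude patients with baseline symptoms or a tube. Some patients may therefore start radiation with a condition that would also be graded afterwards.

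The trial has one arm. With no control group, the patient's own baseline is the only internal means of telling the effects of disease and surgery from those of treatment. If that baseline is never graded, a rate of late dry mouth or hoarseness cannot be read as a rate of treatment-emergent toxicity. Any decision at analysis to leave out pre-existing cases would be an unplanned judgement.

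**Working it through.** **1. The plan's own design figure.** The only operating characteristics in Section 14.0 are for the primary rule (at least 14 of 19; 40% against 90%). Exact binomial: P(X ≥ 14 | 19, 0.40) = 0.0031 and P(X ≥ 14 | 19, 0.90) = 0.9914. These match the stated type 1 error below 0.01 and power of 0.99. Nothing below changes them, and no precision target is stated for toxicity.

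**2. Is there a baseline grade or a worsening rule?** Side by side:
- Section 11.0: grading during radiation.
- Schedule table in Section 10.2: adverse event row blank before treatment.
- Section 8.1: no symptom grading in the pre-treatment lists.
- Section 11.1: late toxicity defined by timing only.
- Section 14.0: sample proportion, with no comparison with baseline.
- Section 17.3: relationship to treatment is listed as content of serious adverse event reports. No attribution is specified for non-serious dry mouth or hoarseness.

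So no baseline grade is scheduled, and no rule either includes or excludes pre-existing conditions.

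**3. Which toxicities are exposed?**
- Dry mouth: no baseline measure is named.
- Hoarseness: no voice measure; only what the history or examination happens to record.
- Feeding tube: no field; only the history.
- Dysphagia: objective baseline, repeated at 6, 12, 18 and 24 months. It yields no CTCAE grade and is not linked to the CTCAE rates.

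**4. The one example in the documents.** Section 3.0 reports late gastrostomy tube use in 4 of 66 patients, "though 2 of these patients had the percutaneous endoscopic gastrostomy tube placed prior to EBRT".
- All tubes: 4/66 = 6.1% (exact 95% CI 1.7 to 14.8), which reproduces the stated 6.1%.
- Without the 2 earlier tubes, full denominator: 2/66 = 3.0% (0.4 to 10.5).
- Denominator limited to patients without an earlier tube: 2/(66 − 2) = 2/64 = 3.1% (0.4 to 10.8).

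Half of the reported late tube use predated radiotherapy. With 4 events the intervals overlap widely, so this illustrates the mechanism and does not estimate its size in this trial.

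**5. Size per patient here.** 1/19 = 5.3 percentage points for each unchanged pre-existing condition that is counted.

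**6. Range under assumptions.** Let b be the baseline prevalence of a condition and t the treatment-emergent rate among patients free of it at baseline. If every baseline case persists and is counted, the apparent rate is b + (1 − b)t, and the expected excess is 19·b·(1 − t) patients. The documents give neither b nor t for dry mouth or hoarseness, so both are assumed. With t = 10%:

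| b (assumed) | Apparent rate | Excess patients of 19 |
|---|---|---|
| 0% | 10.0% | 0 |
| 5% | 14.5% | 0.9 |
| 10% | 19.0% | 1.7 |
| 20% | 28.0% | 3.4 |
| 30% | 37.0% | 5.1 |

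For example, at b = 20%: 0.20 + 0.80 × 0.10 = 0.28, and 19 × 0.20 × 0.90 = 3.42.

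**The case against.** A reader might infer that the plan counts pre-existing conditions as treatment toxicity. The documents do not support this. Section 14.0 speaks of toxicities. Sections 11.1 and 11.2 discuss them under headings that tie them to radiation or chemoradiation, and Section 11.1 refers to events that occur after radiation. The plan is silent on the counting rule; it does not adopt a wrong one. That objection stands, so the claim can only be that such conditions may be counted.

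Further points in the plan's favor:
- **Baseline information exists.** History, examination, co-morbidities and a mandatory swallowing study are all collected. This largely answers the concern for dysphagia. It does not answer it for dry mouth or hoarseness, where no measure or grade is specified.
- **Early weekly checks approximate a baseline.** This is partly right, but they fall after radiation has begun, doxorubicin is given from week 1, and no text names the first check as the reference.
- **Tube timing can be recovered from records.** The retrospective series did so and disclosed it. A reader should therefore not infer that nothing can be reconstructed. Mild symptom grades are harder to recover from notes than the date of a tube.
- **A tube before IMRT need not reflect disease or earlier surgery.** Section 9.2.5 would also cover one placed in anticipation of treatment. This is why the reason for the tube should be recorded.
- **Grade threshold matters.** A stable grade 2 symptom does not enter a grade 3 rate. Section 14.0 names no threshold, so the exposure depends on what is reported.
- **The rates are secondary and descriptive,** with no decision rule attached. This limits the consequence.

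**Conclusion.** The point holds in a limited form. The plan schedules no CTCAE grade before radiation and has no rule to separate pre-existing from new or worsened conditions, so the crude acute and late rates may include baseline dry mouth, hoarseness and feeding tubes. Any such inclusion can only raise the rates as measures of treatment-emergent toxicity.

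The step of 5.3 points per counted patient follows from the denominator of 19. The number of such patients is unknown, and the table of apparent rates rests on assumed prevalences, on persistence of every baseline case and on all of them being counted. It should not be read as an estimate of actual bias. Sample size, type 1 error and power are unaffected. The change is a cheap improvement worth making because toxicity capture is a stated purpose and a missing baseline grade cannot be reliably filled in at analysis.

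**What to change.** - **Schedule table (Section 10.2) and Section 8.1:** mark adverse event monitoring in the pre-treatment column. At the history and physical already required within 30 days, record CTCAE v4.0 grades for dry mouth, hoarseness, dysphagia and other head-and-neck symptoms, and whether and why a feeding tube is in place.
- **Section 11.0:** align the sentence on when grading starts with the revised table.
- **Section 14.0:** for each acute and late toxicity, report the proportion of patients whose grade exceeds their own baseline, beside the crude proportion. Keeping the crude rate preserves total symptom burden and comparability with the institution's earlier series. List tubes placed before IMRT separately.
- **Patients already treated, including the 8 given IMRT alone:** abstract baseline status from the chart where possible and flag it as retrospective.

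The cost is a few fields on an existing visit form and one or two sentences in Section 14.0. The downside is that baseline grades for patients already treated will be less reliable. Treatment, sample size and the primary analysis do not change.
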